#### 11.1.3 Non-Measurable Disease

Non-measurable disease is defined as either uni-dimensionally measurable lesions, masses with margins not clearly defined, or lesions with maximal perpendicular diameter <10mm.

## **11.1.4** Target Lesions

All measurable lesions up to a maximum of 5 lesions should be identified as target lesions and recorded and measured (sum of the products of the perpendicular diameters) at baseline. Target lesions should be selected on the basis of their size (lesions with the longest diameters) and their suitability for accurate repeated measurements by imaging techniques. Occasionally, the largest lesions may not be suitable for reproducible measurement and the next largest lesions which can be measured reproducibly should be selected.

#### 11.1.5 Non-Target Lesions

For participants with recurrent disease who have multiple lesions of which only one or two are increasing in size, the enlarging lesions should be considered the target lesions for evaluation of response. The other lesions will be considered non-target lesions and should also be recorded.

Rarely, unequivocal progression of a non-target lesion requiring discontinuation of therapy, or development of a new contrast-enhancing lesion may occur even in the setting of stable disease (SD) or partial response (PR) in the target lesions. These changes would qualify as progression.

Non-target lesions also include measurable lesions that exceed the maximum number of 5.

Measurements of these lesions are not required but the presence or absence of each should be noted throughout follow-up.

11.1.6 Guidelines for Evaluation of Measurable Disease

All measurements should be taken and recorded in metric notation using a ruler or calipers. All baseline evaluations should be performed up to 28 days before the beginning of the treatment.

Conventional MRI is required, CT is not acceptable. The same method of assessment and the same technique should be used to characterize each identified and reported lesion at baseline and during follow-up. These techniques should be performed with contiguous cuts of 10mm or less in slice thickness. The MRIs will be evaluated both locally and centrally by a core lab.

## **11.2** Response Criteria for Target Lesions

**11.2.1** Complete response (CR:): All of the following criteria must be met:

- a) Complete disappearance of all enhancing measurable and non-measurable disease sustained for at least 4 weeks
- b) No new lesions
- c) Stable or improved non-enhancing (T2/FLAIR) lesions
- d) Participants must be off corticosteroids
- e) Stable or improved clinically

**11.2.2** Partial response (PR): All of the following criteria must be met:

- a) Greater than or equal to 50% decrease compared to baseline in the sum of products of perpendicular diameters of all measurable enhancing lesions sustained for at least 4 weeks
- b) No progression of non-measurable disease
- c) No new lesions
- d) Stable or improved non-enhancing (T2/FLAIR) lesions on same or lower dose of corticosteroids compared to baseline scan
- e) The corticosteroid dose at the time of the scan evaluation should be no greater than the dose at time of the baseline scan
- f) Stable or improved clinically
- **11.2.3** Stable disease (SD): All of the following criteria must be met:
  - a) Does not qualify for CR, PR, or progression
  - b) Stable non-enhancing (T2/FLAIR) lesions on same or lower dose of corticosteroids compared to baseline scan
  - c) Stable clinically
- **11.2.4** Progressive disease (PD): Any of the following criterion must be met:
  - a)  $\geq 25\%$  increase in the sum of products of perpendicular diameters of enhancing lesions compared to the smallest tumor measurement obtained either at baseline (if no decrease) or best response, on stable or increasing doses of corticosteroids
  - b) Significant increase in T2/FLAIR non-enhancing lesion on stable or increasing doses of corticosteroids compared to baseline scan or best response following initiation of therapy, not due to co-morbid events (e.g. radiation therapy, demyelination, ischemic injury, infection, seizures, post-operative changes, or other treatment effects)
  - c) Any new lesion

- d) Clear clinical deterioration not attributable to other causes apart from the tumor (e.g. seizures, medication side effects, complications of therapy, cerebrovascular events, infection, etc.) or changes in corticosteroid dose
- e) Failure to return for evaluation due to death or deteriorating condition
- f) Clear progression of non-measurable disease.

The RANO Response Criteria are summarized in Table 5.

Table 5: Summary of RANO Response Criteria.

	CR	PR	SD	PD#
T1-Gd +	1-Gd + None		<50% decrease to <25% increase	≥25% increase*
T2/FLAIR	Stable or decrease	Stable or decrease	Stable or decrease	Increase*
New Lesion	None	None	None	Present*
Corticosteroids	None	Stable or decrease	Stable or decrease	NA
Clinical Status	Stable or increase	Stable or increase	Stable or increase	Decrease*
Requirement for Response	All	All	All	Any*

CR=complete response; PR=partial response; SD=stable disease; PD=progressive disease; NA= not applicable # Progression occurs when any of the criteria with \* is present

NA Increase in corticosteroids alone will not be taken into account in determining progression in the absence of persistent clinical deterioration

#### **11.3** Confirmatory Measurement/Duration of Response

#### 11.3.1 Confirmation

To be assigned a status of PR or CR, changes in tumor measurements must be confirmed by repeat assessment that should be performed at least 4 weeks after the criteria for response are first met.

#### **11.3.2 Duration of Overall Response**

The duration of overall response is measured from the time criteria are met for CR or PR until the first date that recurrent or progressive disease is objectively documented (taking as reference for progressive disease the smallest measurements recorded since the treatment started).

#### **11.3.3 Duration of Stable Disease**

Stable disease is measured from the start of the treatment until the criteria for progression are met, taking as reference the smallest measurements recorded since the treatment started.

## 11.4 Modified RANO (iRANO): Study Continuation Beyond Initial Progressive Disease

Immunotherapeutic agents such as VB-111 may produce antitumor effects by potentiating endogenous cancer-specific immune responses which may manifest as initial worsening of enhancement and edema on MRI (i.e. pseudoprogression). In addition, the response patterns seen with immunotherapies may extend beyond the typical time course of responses seen with cytotoxic agents, and can manifest a clinical response after an initial increase in tumor burden or even the

appearance of new lesions. For these reasons, the immune-related response criteria (irRC) have endorsed continuation of study therapy beyond initial radiographic evidence of progression for clinically stable participants undergoing immune based therapies [56].

A major advance of the RANO criteria [55] to assess response in neuro-oncology over the previously used Macdonald criteria [57] includes recognition of the prevalence of pseudoprogression during the first three months following completion of radiation and daily temozolomide [58, 59]. Specifically, RANO permits participants with such progressive MRI findings to continue temozolomide therapy for up to three months in order to avoid inaccurately classifying such participants as progressive. Furthermore, RANO permits participants with progressive radiographic findings to continue current therapy pending follow-up imaging if the etiology of progressive imaging findings is unclear. Standard RANO may not provide an accurate response assessment of immunotherapeutic agents such as VB-111.

Therefore, the following adaptations of the RANO criteria will be used to assess response for participants treated on this study in an exploratory fashion (Table 6):

• Potential Pseudoprogression: If radiologic imaging shows initial PD, participants who are not experiencing significant clinical decline (e.g. significant decrease in KPS), may be allowed to continue study treatment until progression is supported by two consecutive time points of tumor growth. Participants should be closely monitored with MRIs every cycle (approximately every 6 weeks) during this period. Participants who have radiographic evidence of further progression after up to three months, or who decline significantly at any time, will be classified as progressive with the date of disease progression back-dated to the first date that the participant met criteria for progression and such participants will be discontinued from study therapy. Although the kinetics of pseudoprogression due to immune therapy among glioblastoma participants is currently unknown, three months is a reasonable estimate based on: 1) the peak time for XRT/daily temozolomide-related pseudoprogression is usually within three months of completion for glioblastoma participants [56, 57] and; 2) three months is also the most common timeframe for pseudoprogression observed among participants with advanced melanoma or other solid tumors treated with immune therapies such as immune checkpoint blockade to date [60-62].

Among participants on this study with initial radiographic PD, tumor assessment should be repeated regularly (approximately every 6 weeks) in order to confirm PD with the option of continuing treatment and the addition of bevacizumab or biosimilar while awaiting radiologic confirmation of progression.

Participants who have progression that is supported by two consecutive time points of tumor growth will discontinue study medication and enter the follow up/survival phase of the study. In determining whether or not the tumor burden has increased or decreased, investigators should consider all target lesions as well as non-target lesions.

• Tumor Enhancement to Define Progression: RANO expanded the previously utilized Macdonald criteria to include the development of "significantly" increased T2 or FLAIR abnormality in the definition of progressive disease because such changes can be a major component defining radiographic progression following therapeutic use of VEGF/VEGFR-targeting therapeutics which are known to elicit potent anti-permeability changes that limit contrast uptake. However, immune based therapies are expected to be associated with

inflammatory changes that may include edema. Therefore, radiographic progressive disease will be defined by assessment of enhancing tumor and will not declare tumor progression based on the presence of T2 or FLAIR changes alone as outlined in RANO because:

- There is no expectation that immunotherapy agents will falsely diminish enhancing tumor burden as has been noted with anti-angiogenic therapies; and
- Immune based therapies are expected to induce inflammatory responses which may be associated with increased edema and T2/FLAIR changes. Such radiographic finding may inaccurately be interpreted to represent tumor progression (i.e. pseudoprogression).

In participants who have initial evidence of radiographic PD, it is at the discretion of the treating physician whether to continue a participant on study treatment for up to three months pending confirmation of PD on follow-up imaging. This clinical judgment decision should be based on the participant's overall clinical condition, including performance status, clinical symptoms, and laboratory data. Participants may receive bevacizumab or biosimilar 10mg/kg2 every 2 weeks in addition to study treatment while waiting for confirmation of PD if they are not experiencing significant clinical decline and the participant is adequately tolerating study therapy (if a participant is required to discontinue study treatment for toxicity as defined per protocol section 5, then they must be taken off-treatment).

When feasible, study therapy should not be discontinued until progression is supported by two consecutive time points of tumor growth. This allowance to continue treatment despite initial radiologic progression takes into account the observation that some participants can have a transient tumor flare in the first few months after the start of immunotherapy, but with subsequent disease response [49]. Participants that are exhibiting significant neurologic decline are not required to have repeat imaging for confirmation of progressive disease.

A randomized, placebo controlled phase II, surgical trial to evaluate early immunologic pharmacodynamic parameters for the viral cancer therapy ofranergene obadenovec (VB-111) in patients with surgically accessible recurrent/progressive glioblastoma Version 3.0 February 18, 2021

able 0. illiagi	able 6: Imaging and Treatment After 1st Radiographic Evidence of PD.							
	No Significant Neuro	ologic Decline	Significan	Significant Neurologic Decline				
	Imaging	Treatment	Imaging	Treatment				
$1^{st}$	Repeat imaging (every	May continue	Repeat imaging	May continue study				
radiologic	cycle, approximately	study treatment	6 weeks later to	treatment and start				
evidence of	every 6 weeks)	at the	confirm PD if	bevacizumab or biosimilar				
PD	for up to 3 months to	Investigator's	possible	10mg/kg Q2 weeks until				
	confirm PD	discretion for		the next scheduled				
		up to 3 months		imaging assessment. A				
		while awaiting		washout period of 2 weeks				
		confirmatory		between VB-111 and				
		imaging		bevacizumab or biosimilar				
		assessment		doses is recommended.				
Repeat scan	No additional imaging	Discontinue	No additional	Discontinue treatment				
up to 3	required; date of	treatment	imaging					
months after	tumor progression		required; date of					
$1^{st}$	back-dated to date of		tumor					
radiologic	initial radiographic PD		progression					
evidence			back-dated to					
confirms			date of initial					
PD			radiographic PD					
Repeat scan	Continue	Continue study	Continue	May continue study				
shows SD,	regularly	treatment at the	regularly	treatment and continue				
PR or CR	scheduled	Investigator's	scheduled	bevacizumab or biosimilar				
	imaging	discretion	imaging	indefinitely. A washout				
	assessments		assessments	period of 2 weeks between				
	every 6 weeks		every	VB-111 and bevacizumab				
			6 weeks	or biosimilar doses is				
				recommended,				

Table ( Incasing and	Turatura ant After	1 at Dadia ananhi	- Erridanas of DD
Table 6: Imaging and	Treatment After	1st Radiographi	c Evidence of PD.

A participant may be granted an exception to continue on treatment with confirmed radiographic progression if clinically stable or clinically improved. The exception will be granted following discussion with Sponsor and VBL.

Participants with progressive radiographic findings are encouraged to undergo surgical intervention in order to delineate pseudoprogression due to inflammation associated with VB-111 from true tumor progression. Participants with histopathologic findings of significant immune infiltrate and evolving gliosis will be allowed to continue study therapy. In contrast, those with clear evidence of progressive tumor by histopathologic evaluation will be defined as progressive and discontinued from study therapy. For such participants, the date of tumor progression will be the first date the participant met radiographic criteria for PD.

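### Section 11.4 gives conflicting instructions for participants who decline significantly at or after first radiographic progression: the text discontinues them and counts them as progressive, while Table 6 lets them continue and be re-assessed

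*Combined protocol and SAP*

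**What the plan says.** Four statements in the Section 11.4 text bear on a participant with first radiographic progression (PD).

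- Continuation: "participants who are not experiencing significant clinical decline (e.g. significant decrease in KPS), may be allowed to continue study treatment". Those who show further growth, "or who decline significantly at any time, will be classified as progressive", with the date set back to when the criteria were first met, and "such participants will be discontinued from study therapy".
- Bevacizumab, first statement: repeat assessment is described "with the option of continuing treatment and the addition of bevacizumab or biosimilar while awaiting radiologic confirmation of progression", with no condition on decline.
- Bevacizumab, second statement: it may be given "while waiting for confirmation of PD if they are not experiencing significant clinical decline".
- Imaging: "Participants that are exhibiting significant neurologic decline are not required to have repeat imaging for confirmation of progressive disease".

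Table 6 then splits participants by neurologic decline. In the decline column at first PD, the imaging cell asks for a repeat scan 6 weeks later if possible. The treatment cell permits continued study "treatment and start" of bevacizumab or a biosimilar until the next scheduled scan. If the repeat scan confirms PD, treatment stops and the date is set back to the initial PD. If it shows SD, PR or CR, both study treatment and bevacizumab may go on, the latter without a time limit.

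Elsewhere, Section 5.1 allows VB-111 to continue after contrast-enhancing progression in Groups A and B provided the participant is clinically stable. Section 1.1 has VB-111 continuing until growth is seen on two successive assessments, with no stability condition. Section 5.7.5 allows bevacizumab for edema or mass effect for as long as the investigator judges it necessary.

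**The concern.** The rule decides whether a deteriorating participant receives further investigational gene therapy, and in which direction the iRANO assessment goes. In a multicentre trial, two sites could handle identical participants in opposite ways and each cite Section 11.4 in support. A monitor would have no single rule against which to judge a deviation. Post-operative treatment is unblinded (Section 5.4), so discretionary differences in handling are not masked.

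Safety is a primary objective (Section 1.2), and adverse events are collected for 30 days and serious adverse events for 90 days from the last dose (Section 7.5). The choice of rule therefore changes both cumulative exposure and the period over which events are counted. It can also change whether a participant counts as progression-free under iRANO.

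**Working it through.** The plan gives no figure to reproduce here. The check is a side-by-side reading for one participant who has first radiographic PD and significant decline.

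| Item | Section 11.4 text | Table 6, decline column |
|---|---|---|
| Study treatment at first PD | Discontinued | May continue |
| Bevacizumab while waiting | One sentence without a condition; one conditional on no significant clinical decline | May start |
| Repeat scan | Not required | Requested at 6 weeks if possible |
| Repeat scan confirms PD | Already progressive, back-dated; already off treatment | Progressive, same back-dated date; stops now |
| Repeat scan shows SD, PR or CR | Progressive, back-dated; off treatment | Not declared progressive; may stay on treatment and bevacizumab |

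**Treatment.** The two rules differ whatever the repeat scan shows.

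**Progression status.** They differ only in the last row. When PD is confirmed, both give the same date. The table has no row for a decliner who is not re-scanned, so there it assigns no status.

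**No-decline column.** Text and table agree on discretionary continuation for up to three months, on scans about every 6 weeks, and on stopping with a back-dated date once PD is confirmed. The table does not mention bevacizumab in this column.

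**Exposure, by way of illustration (Groups A and B).** Assume infusions and scans every 6 weeks on schedule, with each scan read before dosing. Let the last infusion before PD be day 0, so the scan showing PD falls on day 6 × 7 = 42.

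- Text: the last infusion stays at day 0. The windows close at day 30 (adverse events) and day 90 (serious adverse events).
- Table: an infusion may be given at day 42. The windows close no earlier than 42 + 30 = day 72 and 42 + 90 = day 132.

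That is one further infusion and a shift of at least 42 days, with more if the repeat scan is not confirmatory.

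**Effect on iRANO PFS6 of one participant whose status differs.** With the planned 15 per group (Section 5.1):

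- one group: 1/15 = 0.067, or 6.7 percentage points;
- Groups A and B pooled: 1/30 = 0.033, or 3.3 percentage points.

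**Endpoints not reached.** TIL density is measured on tissue from the protocol surgery, before these rules can apply. Secondary PFS6 uses RANO (Sections 1.3 and 13.1.1), where clear clinical deterioration attributable to the tumor is already PD (Section 11.2.4, item d). The iRANO PFS6 and PFS are exploratory (Section 1.4).

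**The case against.** Three arguments could be made that there is no conflict.

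1. The continuation rule speaks of clinical decline and Table 6 of neurologic decline, so they may address different participants. This does not hold. Neither term has a threshold, the 11.4 text itself uses "significant neurologic decline", and the discontinuation sentence covers any significant decline.
2. Section 11.4 leaves continuation to the treating physician's judgement. It does so in general, but the sentence on decliners is mandatory, so discretion cannot satisfy both.
3. The table might be taken as the operative rule because the text refers to it. Nothing gives it precedence, and Section 5.1 sides with the text.

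Other objections do stand, and they rule out four stronger readings.

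- A reader might infer that text and table are opposite in both columns. They are not: the no-decline column agrees with the text on treatment, imaging and dating, and silence on bevacizumab is not a prohibition.
- A reader might infer that the protocol bars bevacizumab in anyone who declines and that Table 6 overturns the bar. The restriction rests on one sentence. Another sentence in Section 11.4 has no such condition, and Section 5.7.5 permits bevacizumab for edema with new or worsened neurologic deficit.
- A reader might apply the 6.7 points to the secondary PFS6. That endpoint uses RANO, and Table 6 does not alter its definition.
- A reader might infer that every decliner's progression status is in doubt. It differs only where the repeat scan does not confirm PD.

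**Conclusion.** The contradiction is real, and no other section resolves it. For a participant who declines significantly at or after first radiographic PD, the Section 11.4 text requires discontinuation and a progressive classification, while Table 6 permits continuation, with status left to a repeat scan. Section 5.1 conflicts with the table as well. The bevacizumab part is weaker: it is a set of inconsistent statements, not a ban that is later reversed.

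Treatment exposure and the safety window are affected for every such participant. Exploratory iRANO PFS6 and PFS status are affected only when the repeat scan does not confirm PD. The 6.7-point and 3.3-point figures are for scale and assume denominators of 15 and 30. Section 5.6 allows additional recruitment to reach 15 evaluable per arm, so the number randomized may be larger and the step smaller. The documents do not give the expected number of such participants, so the total effect cannot be estimated.

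TIL density and the RANO definition of secondary PFS6 are unchanged. Different amounts of post-progression treatment could still influence OS and second PFS, but the size of that cannot be derived from the documents.

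This should be corrected because opposite treatment instructions apply to vulnerable participants. The statistical consequence alone is modest.

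**What to change.** Reconcile the Section 11.4 text, Table 6, Section 5.1, Section 1.1 and Section 5.7.5 so that one rule governs three things after significant decline: continuation of study treatment, addition of bevacizumab, and confirmation imaging. Amending Section 11.4 alone would leave the differing conditions in Sections 1.1 and 5.1 in place. Use one defined term for decline throughout.

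For the chosen rule, state the iRANO status and progression date in each case: repeat scan confirms PD, repeat scan shows SD, PR or CR, and no repeat scan done. State also whether the bevacizumab condition applies only to use while awaiting confirmation or also to supportive use under Section 5.7.5.

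Which rule to adopt is a clinical decision for the sponsor and is not proposed here. The cost is amendment wording, with no added procedures.
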